The serological findings related to IgG4 concentrations are supported by flow cytometry investigations. Serial flow cytometry studies on all six patients demonstrate swift, nearly complete depletions of the cell types of interest: namely, the CD4+ and CD8+ cytotoxic T lymphocytes, plasmablasts, and DN3 B cells. Steep declines of each cell type were observed quickly following receipt of elotuzumab, often by 48 hours following the first infusion. These cells begin to re-constitute at varying intervals, averaging approximately 6 weeks across the 6 patients and occurring earlier for the patient with early clinical relapse.

The transient depleting effect of elotuzumab observed in IgG4-RD is consistent with the therapeutic strategy developed for multiple myeloma. Our observations in Part 1A suggest that re-treatment of patients with elotuzumab at some regular interval will be required. This fits the pattern of treatment with other monoclonal antibodies for other autoimmune diseases, most of which require re-treatment on some regular basis. As examples, re-treatment with infliximab every six weeks is a standard treatment approach for Crohn's disease, rheumatoid arthritis, and ankylosing spondylitis.

Because clinical manifestations of active IgG4-RD generally trail serological elevations in IgG4 concentrations, modifications to Parts 1B and 2 of the protocol will include the infusion of elotuzumab every eight weeks starting at Baseline/Day 0, and followed by infusions at Weeks 8, 16, 24, 32, and 40. This elotuzumab + 10-week prednisone taper appears likely to establish disease control in a substantial majority of patients treated in this fashion. Regularly planned re-treatment of patients in Part 1B will permit important insights into the potential efficacy of every 8-week elotuzumab infusions for the maintenance of remission.

Finally, the observations from Part 1A also underscore the importance of blinding both the investigators and participants to serum IgG4 concentrations in the randomized, double-blind part of the elotuzumab in IgG4-RD trial program.

2 Study Hypotheses/Objectives

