Mechanistic studies will also be performed on a subset of participants (MGH participants only) with submandibular gland involvement at baseline who consent to follow-up submandibular gland biopsies. Biopsies for immunohistochemical studies will be performed using standard core needle biopsy techniques. The purpose of these studies will be to determine the effects of study therapy on the chronic inflammatory response at a site of tissue inflammation in submandibular glands. For Part 1A, submandibular gland samples will be obtained prior to Baseline/Day 0 and between Weeks 16 and 24 following the Baseline/Day 0 visit. For Part 1B and 2, submandibular gland samples will be obtained prior to the Baseline/Day 0 Visit, following eligibility confirmation ,and between Weeks 40 and 44 following the Baseline/Day 0 visit. Paraffin-embedded sections will be stained with antibodies to identify T cells, B cells, macrophages, dendritic cells, cytokines, and chemokines.

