8.1 Visit Windows

Appendix 1 presents the Schedule of Events Tables for Part 1 and Part 2. The date for all visits are calculated relative to the date of the Baseline/Day 0 Visit. The visit windows are defined below:

Part 1A:

- Screening until Baseline/Day 0: 28 days from time of obtaining informed consent until randomization and initiation of study treatment
- Weekly infusion visits*: + 3 days / - 1 day
- Every 2-week infusion visits: \pm 3 days

Monthly follow-up visits: \pm 5 days

* Weekly infusion visits must be scheduled to allow for a minimum of four full days between infusions.

Part 1B and 2:

- Screening until Baseline/Day 0: 28 days from time of obtaining informed consent until randomization and initiation of study treatment
- Day 7: \pm 2 days
- Safety Visits (Weeks 4, 12, 20, 28, 36, 44, 48): \pm 7 days
- Infusion Visits (Weeks 8, 16, 24, 32, 40): \pm 7 days

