9.3 Effect of Elotuzumab at the Tissue Level

We will determine whether elotuzumab achieves tissue-level depletion of SLAMF7-expressing lymphocyte subpopulations by examining pre- and post-treatment submandibular gland biopsies by multi-color immunofluorescence to quantify infiltrating CD4+CTLs, activated B cells, and plasma cells.

During Part 1A, an optional core biopsy of the submandibular gland will be performed at the Baseline visit and again between Weeks 16 and 24 to evaluate the tissue response to study therapy. During Part 1B and 2, an optional submandibular gland biopsy will be performed prior to the Baseline/Day 0 Visit, following eligibility confirmation, and between Weeks 40 and 44. The participants will be instructed to suspend aspirin or NSAID intake 3-7 days before the procedure. Core biopsy of the submandibular gland is generally only slightly painful and rarely associated with significant morbidity. However, it is possible that a biopsy site might become infected, requiring antibiotic treatment or surgical debridement. After application of a topical anesthetic, local anesthetic with vasoconstrictor is infiltrated into the skin and subcutaneous tissues external to the submandibular gland. The biopsy is then performed with a large-gauge biopsy needle. The biopsy obtained will be preserved in saline for additional studies.

We will examine submandibular gland biopsies by multi-color immunofluorescence to quantify infiltrating CD4+CTLs, activated B cells, and plasma cells. We hypothesize that elotuzumab will achieve tissue-level depletion of SLAMF7-expressing lymphocyte subpopulations and this will correspond with clinical improvement. For control salivary gland tissue, we will obtain fresh, disease-free margins from the MGH Surgery Department from participants undergoing salivary gland resection. Tissue samples will be fixed in formalin, embedded in paraffin and sectioned. Sections will be incubated with antibodies specific for CD4, CD8, SLAMF7, TGF- β , GZMA, IFN- γ , CD19, CD27, IgD, CD38, CD138, IgG4 and CD57. Lymphocyte subpopulations will be quantified using TissueQuest Software. In addition to demonstrating the tissue-level effects of elotuzumab in comparing the pre- and post-treatment samples, the pre-treatment samples will also allow accurate quantification of cell-cell interactions by measuring inter-nuclear distances.

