³ Imaging required to complete a full IgG4-RD RI assessment will be performed for the Screening visit. Specifically, all participants will undergo either a CT or MRI of the chest, abdomen, and pelvis at Screening. Participants with clinical evidence of orbital disease will also undergo CT or MRI of that area. If abnormalities in a particular area are detected at Screening, the participant will have the same type of study repeated at Week 48. Imaging at week 48 will be performed if there is a clinical reason to suspect disease activity at that site. Imaging may also be repeated at the discretion of the investigator at a visit other than those two time points if required to assess disease activity because of a potential disease flare or to assess an adverse event.

^{3a} Oral or intravenous contrast agents may be used in some radiology studies. The need for contrast agents will be reviewed on an individual basis, consistent with the routine use of these imaging studies. Consultation with radiology will be obtained as needed.

⁴ eGFR to be calculated centrally per the CKD-EPI formula.

⁵ ELF Score serology: TIMP-1, PIIINP, HA.

⁶ By Interferon-Gamma Release Assay (IGRA) at or within 90 days of the Screening visit. If indeterminate, repeat (with same or other IGRA per local policy) or obtain PPD (the later to be read within 48-72 hours and may be read locally with documentation of result by health care provider). If history of BCG vaccine or other complication in interpretation of result, consultation with ID is required for clearance to proceed.

⁷ HIV, Hepatitis B surface antigen and Hepatitis B core antibody, Hepatitis C antibody.

⁸ U/A macroscopic and microscopic analysis, culture if indicated.

⁹ For women of child-bearing potential. Stat urine HCG prior to each infusion may be performed locally with point of care testing.

¹⁰ Submandibular gland biopsy: fine needle aspiration of parotid or submandibular salivary gland. Sub-study to be conducted only at MGH. May use tissue previously acquired if available. Opt-out language to be included in the informed consent document.

^{10a} Submandibular gland biopsy may be obtained between Week 40 and 44.

¹¹ To be obtained stat locally and reviewed before each infusion (or within 72 hours of subsequent infusion).

^{11a} Safety labs should be repeated at Baseline/Day 0 after screening only as clinically indicated.

¹² To be completed only at visits following a flare occurrence.

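### In Parts 1B and 2 the post-treatment gland biopsy window opens on the Week 40 infusion visit with no stated order, so samples 8 weeks and 0 to 4 weeks after drug are pooled; footnote 10 also contradicts the body text on technique and gland

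*Combined protocol and SAP*

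**What the plan says.** **Timing.** Section 3.6.6 places the Part 1B/2 gland samples before Baseline "and between Weeks 40 and 44 following the Baseline/Day 0 visit". Sections 6.5 and 9.3 and footnote 10a of the Part 1B/2 schedule ("Submandibular gland biopsy may be obtained between Week 40 and 44") agree. The schedule marks the biopsy at both the Week 40 and Week 44 visits and marks an infusion at Week 40. Section 1.5.1 gives the dosing as "the infusion of elotuzumab every eight weeks starting at Baseline/Day 0, and followed by infusions at Weeks 8, 16, 24, 32, and 40". Section 8.1 allows ±7 days on infusion visits.

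**Expected cell kinetics.** Section 1.5.1 reports steep declines of the target cells in blood in the six Part 1A patients, "often by 48 hours following the first infusion". The cells began to return at about 6 weeks on average.

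**Technique and gland.** Footnote 10, in both schedules, reads "Submandibular gland biopsy: fine needle aspiration of parotid or submandibular salivary gland". Section 3.6.6 says "Biopsies for immunohistochemical studies will be performed using standard core needle biopsy techniques". Sections 6.5 and 9.3 also describe core biopsy of the submandibular gland, and 9.3 adds a large-gauge needle, paraffin sections and multi-color immunofluorescence.

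**Use.** The samples serve mechanistic hypothesis 2 (depletion in tissue) and exploratory endpoint 5 (tissue concentrations by arm, before and after treatment).

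**The concern.** A post-treatment sample is meant to show whether the drug clears SLAMF7-expressing cells from the gland. If clearance wanes between doses, the answer depends on when in the dosing cycle the tissue is taken. Here one visit can yield a sample at the end of a cycle or at the start of the next, and both enter the analysis as the same measurement. In a small substudy that variation will not average out, and a result showing little depletion would be hard to interpret.

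The order also changes recent glucocorticoid exposure. Section 6.1.4.2.1 gives intravenous methylprednisolone before every infusion, active or placebo.

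The footnote raises a different problem. A site working from the schedule would perform a different procedure, possibly on a different gland, from a site working from the body text.

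**Working it through.** **Inputs**
- Infusions at Weeks 0, 8, 16, 24, 32 and 40 (Section 1.5.1 and the schedule).
- Infusion visit window ±7 days (Section 8.1).
- Biopsy window Week 40 to Week 44, that is Day 280 to Day 308.
- Return of target cells in blood: about 6 weeks on average (Section 1.5.1).

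**Step 1, the plan's own interval.** Successive differences of the infusion weeks are 8, 8, 8, 8 and 8, which reproduces the stated eight-week dosing.

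**Step 2, nominal time since the last infusion.**
- Biopsy before the Week 40 infusion: 40 − 32 = 8 weeks.
- Biopsy after it: 40 − 40 = 0 to 44 − 40 = 4 weeks.

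**Step 3, with the infusion windows.** The Week 32 infusion falls on Days 217 to 231 and the Week 40 infusion on Days 273 to 287.
- Biopsy first: shortest 280 − 231 = 49 days, longest 287 − 217 = 70 days, so 7 to 10 weeks.
- Infusion first: shortest 0, longest 308 − 273 = 35 days, so 0 to 5 weeks.
- If the ±7 days also applies to the biopsy (Days 273 to 315), the ranges become 6 to 10 weeks (273 − 231 = 42 days at the short end) and 0 to 6 weeks (315 − 273 = 42 days at the long end).

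**Step 4, the last permitted infusion.** Section 6.1.4.2.2 bars infusions after Week 44; Section 6.4.2 bars them after Week 40. If a delayed sixth infusion could fall at Week 44, a biopsy just before it would be 44 − 32 = 12 weeks after drug at nominal times, and up to (308 − 217)/7 = 13 weeks with the Week 32 window. The two sections contradict each other and must be reconciled.

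**Step 5, comparison with Part 1A.** The last dose is on Day 21 (Week 3) and the biopsy falls in Weeks 16 to 24, so 16 − 3 = 13 to 24 − 3 = 21 weeks after drug. No infusion falls inside that window. The ambiguity therefore arises only under the Part 1B/2 schedule.

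**Step 6, technique, side by side.**

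| Source | Technique | Gland |
|---|---|---|
| Footnote 10, both schedules | Fine needle aspiration | Parotid or submandibular |
| Section 3.6.6 | Core needle biopsy | Submandibular |
| Section 6.5 | Core needle biopsy | Submandibular |
| Section 9.3 | Core biopsy, large-gauge needle | Submandibular |

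The footnote is the outlier, and an aspirate does not match the paraffin-section immunofluorescence in 9.3. Because it is attached to the whole biopsy row, it covers the pre-treatment samples as well.

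**The case against.** The strongest reply is that endpoint 5 compares randomised, blinded arms that share the same window, so variable timing mainly adds noise and does not favour either arm. A trough biopsy without depletion is also a true trough result, and Section 6.5 states the aim as the tissue response to therapy, not the nadir. Part 1A did not target the nadir either. All of this stands, and it is why the point is minor. It does not remove the problem. The within-patient before-and-after reading has no such protection, Part 1B has no placebo arm, and Section 13.4 does not mention time since infusion.

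Three stronger readings are tempting, and the documents do not support them.

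- *That most trough samples would show no depletion and most later ones would.* Suppose return times are normal with mean 6 weeks and an assumed SD of 2 weeks (range 1 to 3). The share not yet returning would be 84% (75 to 98%) at 4 weeks and 16% (2 to 25%) at 8 weeks. But the 6 weeks is onset of return, in blood, in six patients given four weekly doses, and the part of Section 1.5.1 available for this review does not state its time origin. Counted from Day 0, 6 weeks is only 3 weeks after the Day 21 dose. The 4-week share then becomes P(Z > (4 − 3)/2) = 31%. No tissue kinetics are given, so no such percentage can be relied on.
- *That an aspirate cannot give the planned measures.* No section states what an aspirate can yield. The one plainly spatial measure is tied to baseline tissue: "the pre-treatment samples will also allow accurate quantification of cell-cell interactions by measuring inter-nuclear distances". What stands is the contradiction and the mismatch with 9.3.
- *That reused tissue makes the baseline invalid.* Footnote 10 does allow previously acquired tissue without limit. But the default is a fresh biopsy before Day 0, and up to 60 mg prednisone daily is allowed during screening. Barring reused tissue because of earlier treatment would be stricter than the rule for fresh samples.

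**Conclusion.** The point holds. The Part 1B/2 window allows a sample 8 weeks or 0 to 4 weeks after the last infusion at nominal times, and about 7 to 10 or 0 to 5 weeks with the infusion windows. These intervals lie on both sides of the only timing guide in the plan, the average of about 6 weeks in blood. The exploratory depletion comparison therefore mixes samples that are not comparable. How much this distorts it is unknown without tissue kinetics. The arithmetic assumes the Week 32 and Week 40 infusions are given within their windows; a missed or delayed dose widens the spread.

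The contradiction in footnote 10 needs no assumption.

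Severity is minor. The substudy is optional, runs at one site, has no stated sample size and is exploratory. The primary, key secondary and safety analyses are unaffected.

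**What to change.** - In Sections 3.6.6, 6.5 and 9.3 and footnote 10a, place all Part 1B/2 post-treatment research biopsies on the same side of the Week 40 infusion. Count the window from the actual infusion date, for example a set number of days after it, near the Week 44 visit. Tying it only to the Week 44 visit (±7 days) would still leave 301 − 287 = 14 to 315 − 273 = 42 days, that is 2 to 6 weeks.
- Record time since the last infusion for every biopsy and state how the analysis uses it. This also covers participants who missed the Week 40 dose.
- Reconcile footnote 10 in both schedules with the body text on technique and gland.
- Reconcile Sections 6.1.4.2.2 and 6.4.2 on the last permitted infusion.
- Record the date of, and treatment before, any reused archived tissue.

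The cost is text edits and a narrower booking window. A biopsy near Week 44 also loses the same-visit PBMC and plasma sample, because research blood is drawn at Weeks 40 and 48 and the Week 44 research draw is 0 mL.

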20.2 Appendix 2: ACR/EULAR

The 2019 ACR/EULAR Classification Criteria for IgG4-Related Disease

Step		
1. Entry Criteria	Characteristic* clinical or radiologic involvement of a typical organ (e.g., pancreas, salivary glands, bile ducts, orbits, kidney, lung, aorta, retroperitoneum, pachymeninges, or thyroid gland [Riedel's thyroiditis]) OR pathologic evidence of an inflammatory process accompanied by a lymphoplasmacytic infiltrate of uncertain etiology in one of these same organs.	Yes or No **
2. Exclusion Criteria^o	Domains and Items	
	Clinical	
	Fever	
	No objective response to glucocorticoids	
	Serological	
	Leukopenia and thrombocytopenia with no explanation	
	Peripheral eosinophilia	
	ANCA positive (specifically against proteinase 3 or myeloperoxidase)	
	Positive SS-A (Ro) or SS-B (La) Antibody	
	Positive dsDNA, ribonucleoprotein, or Smith (Sm) Antibody	
	Other disease-specific auto-antibody	Yes or No ***
	Cryoglobulinemia	
	Radiology	
	Known radiologic findings suspicious for malignancy or infection that have not been sufficiently investigated	
	Rapid radiologic progression	
	Long bone abnormalities consistent with Erdheim-Chester disease	
	Splenomegaly	
	Pathology	
	Cellular infiltrates suggesting malignancy that have not been sufficiently evaluated	

SAMPLE

	Markers consistent with inflammatory myofibroblastic tumor	
	Prominent neutrophilic inflammation	
	Necrotizing vasculitis	
	Prominent necrosis	
	Primarily granulomatous inflammation	
	Pathologic features of macrophage/histiocytic disorder	
	Known Diagnosis of the Following:	
	Multicentric Castleman's Disease	
	Crohn's disease or Ulcerative Colitis (if only pancreatobiliary disease is present)	
	Hashimoto's thyroiditis (if only the thyroid is affected)	

If case meets entry criteria and does not meet any exclusion criteria, proceed to step 3.

3. Inclusion Criteria	Domains and Items	Weight [†]
	Histopathology	
	Uninformative biopsy	+ 0
	Dense Lymphoplasmacytic Infiltrate	+ 4
	Dense Lymphoplasmacytic Infiltrate and Obliterative Phlebitis	+ 6
	Dense Lymphoplasmacytic Infiltrate and Storiform Fibrosis with or without Obliterative Phlebitis	+ 13
	Immunostaining[†] (Table 2b)	+ 0-16
	Serum IgG4 Concentration	
	Normal or Not Checked	+ 0
	> Normal but < 2x Upper Limit of Normal	+ 4
	2x to 5x Upper Limit of Normal	+ 6
	≥ 5x Upper Limit of Normal	+ 11

	Bilateral Lacrimal, Parotid, Sublingual, and Submandibular Glands	
	No set of glands is involved	+ 0
	One set of glands is involved	+ 6
	Two or more sets of glands are involved	+ 14
	Chest	
	Not checked or neither of the items listed is present	+ 0
	Peribronchovascular and septal thickening	+ 4
	Paravertebral Band-Like Soft Tissue in the Thorax	+ 10
	Pancreas and Biliary Tree	
	Not checked or none of the items listed is present	+ 0
	Diffuse pancreas enlargement (loss of lobulations)	+ 8
	Diffuse pancreas enlargement and capsule-like rim with decreased enhancement	+ 11
	Pancreas (either of above) and biliary tree involvement	+ 19
	Kidney	
	Not checked or none of the items listed is present	+ 0
	Hypocomplementemia	+ 6
	Renal pelvis thickening/soft tissue	+ 8
	Bilateral renal cortex low density areas	+ 10
	Retroperitoneum	
	Not checked or neither of the items listed is present	+ 0
	Diffuse thickening of the abdominal aortic wall	+ 4
	Circumferential or antero-lateral soft tissue around the infra-renal aorta or iliac arteries	+ 8
4. Total Inclusion Points	A case meets the classification criteria for IgG4-RD if the entry criteria are met, no exclusion criteria are present, and the total points is ≥ 20	

*Refers to enlargement or tumor-like mass in an affected organ except in:

- the bile ducts, where narrowing tends to occur

- in the aorta, where wall thickening or aneurysmal dilatation is typical
- and in the lungs, where thickening of the bronchovascular bundles is common

**If Entry Criteria not fulfilled, then the patient cannot be further considered for classification as IgG4-RD

***If Exclusion Criteria are met, then the patient cannot be further considered for classification as IgG4-RD

† Biopsies from lymph nodes, mucosal surfaces of the gastrointestinal tract, and the skin cannot be considered

‡ Only the highest-weighted item in each Domain is scored

^aAssessment for the presence of Exclusion Criteria should be individualized depending on a patient's clinical scenario.

20.2.1 Immunostaining for ACR/EULAR Classification

Immunostaining (See Table Below and Enter Appropriate Weight)

		IgG4+ Cells/HPF				
IgG4:IgG+ Ratio		0 to 9	Indeterminate	10 to 50	≥50	
	0 to 40%	0	7.3	7.3	7.3	
	Indeterminate	0	7.3	7.3	7.3	
	41-70%	7.3	7.3	14.1	14.1	
	≥70%	7.3	7.3	14.1	16	

Immunostaining weight:

Round the weight to the nearest whole integer

20.3 Appendix 3: IgG4-RD RI

Date: ____ / ____ / ____ Visit: _____ Patient ID: _____

IgG4-RD Responder Index (Version: July 25, 2016)**Scoring Rules**Scoring refers to manifestations of disease activity present in the last 28 days

At the initial assessment, the physician enters a 2 after any active organs/sites and a 0 after uninvolved organs/sites.

At each subsequent assessment, the physician enters a 0-3 score after the organ/site listed.

0 = Normal or resolved

1 = Improved but still present since the previous assessment or improved from initial assessment with no change from previous assessment

2 = Disease activity unchanged from previous assessment

Once an organ or site has improved or worsened, the score of 2 will no longer be used for that organ/site, ie, an improved organ/system will maintain a score of 1 until resolution (score as 0) or worsening (score as 3).

No change from previous assessment will often refer to disease manifestations that require follow-up imaging to assess accurately; ie, a disease manifestation only assessable by imaging will be assumed to be unchanged until such time that repeat imaging demonstrates improvement, worsening, or resolution.

3 = Worsened or new disease manifestation since the last assessment and requirement for additional therapy (intent to treat)

Definitions*Organ/Site score:* The overall level of IgG4-RD activity within a specific organ system*Symptomatic:* Is the disease manifestation in a particular organ system symptomatic? (Y = yes; N = no)*Urgent disease:* Disease that requires treatment immediately to prevent serious organ dysfunction (Y = yes; N = no)(Presence of *urgent disease* within an organ leads to **DOUBLING** of that organ system score)*Damage:* Organ dysfunction that has occurred as a result of IgG4-RD and is considered permanent (Y = yes; N = no)

Organ/Site	Activity			Damage	
	organ/site score	Symptomatic (Y/N)	Urgent (Y/N)	Yes/No	Symptomatic (Y/N)
Meninges					
Pituitary Gland					
Orbital lesion (specify location): _____					
Lacrimal Glands					
Parotid Glands					
Submandibular Glands					
Other Salivary Glands (specify): _____					
Mastoiditis/Middle Ear Disease					
Nasal Cavity Lesions					
Sinusitis					
Other ENT Lesions (example: tonsillitis, pharyngitis): _____					
Thyroid					
Lungs					

SAMPLE

Date: ___ / ___ / ___		Visit: ___		Patient ID: ___		
Organ/Site		organ/site score	Activity		Damage	
	(Check if present):		Symptomatic (Y/N)	Urgent (Y/N)	Yes/No	Symptomatic (Y/N)
Lymph nodes	Lymph node chain					
	Submental					
	Submandibular					
	Cervical					
	Axillary					
	Mediastinal					
	Hilar					
	Abdominal/pelvic					
	Inguinal					
Other lymph node chain: _____						
Aorta/Large Blood Vessels						
Heart/Pericardium						
Retroperitoneal Fibrosis (RPF)						
Sclerosing Mediastinitis						
Sclerosing Mesenteritis						
Pancreas						
Liver						
Bile ducts						
Kidney						
Skin						
Constitutional symptoms not attributable to involvement of a particular organ (weight loss, fever, fatigue caused by active IgG4-RD)						
Other involvement-specify: _____ (consider prostate, breast, gallbladder involvement. Each "other" item is counted separately)						
Other involvement-specify: _____ (consider prostate, breast, gallbladder involvement. Each "other" item is counted separately)						
Other involvement-specify: _____ (consider prostate, breast, gallbladder involvement. Each "other" item is counted separately)						

Total urgent organs: _____

Total Activity Score

Total symptomatic (active) organs: _____

Organ/sites (x 2 if urgent): _____

Total damaged organs: _____

Total symptomatic (damage) organs: _____

Signature of Investigator: _____

Date: ___ / ___ / ___

